Date: February 1st, 2022

Study Protocol and Statistical Analysis Plan

Study Title	A Pilot Study to Assess the Efficacy and Safety of a Novel Device (VIZO Glasses) in the Management of ADHD in Adults
Protocol ID	VIZO_003
ClinicalTrials.gov ID	NCT05777785

Protocol Synopsis

Device Name	VIZO Glasses
Objectives	To Assess the Efficacy and Safety of a Novel Device (VIZO Glasses) in the Management of ADHD in Adults.
Study Group Investigational Group	VIZO Glasses: Eyeglasses with personalized peripheral retinal stimuli
Key Eligibility Criteria	
Inclusion Criteria	
 • Documented history of primary ADHD diagnosis by certified clinicians • Age 18-40 y • Written informed consent • Able and willing to complete all required ratings and assessments
Exclusion Criteria	
 • Any current psychiatric / neurological comorbidity (e.g., epilepsy, Autism, depression, TBI, etc), other than ADHD • ADHD Medications (stimulants, non-stimulants, other) • Neurofeedback, cognitive training
Endpoints	
Primary	
Adult ADHD Self-Report Scale (ASRS) - Total Score at Baseline and 2 Months Follow up
 
The Adult ADHD Self-Report Scale (ASRS) is a self-report instrument that comprises eighteen items that correspond with the DSM-V-TR criteria for ADHD. Subjects are asked to rate 18 symptom items using a 5-point Likert scale ranging from 0 ('Never') to 4 ('Very Often'). Total scores range from 0 to 72, based on the sum of all 18 questions. Higher scores mean more symptoms and higher ADHD's impairments. Lower values represent better outcomes. The ASRS has two subscales that can be used to identify ADHD subtypes - Inattentiveness and Hyperactivity/Impulsivity. Each subscale contains 9 questions.
 
Adult ADHD Self-Report Scale (ASRS) - Inattentiveness Subscale Score at Baseline and 2 Months Follow up
 
The inattentiveness sub-scale of the ASRS measures difficulties with focusing on details, organisation, remembering appointments, making careless mistakes, and concentration. It includes 9 symptom items using a 5-point Likert scale ranging from 0 ('Never') to 4 ('Very Often'). Total scores range from 0 to 36, based on the sum of all questions. Higher scores mean more symptoms and higher inattentiveness' impairments.

Protocol Synopsis


Secondary
	
Clinical Global Impression-Improvement (CGI-I) - Rate at 2 Months Follow up Based on an interview with the participant, the clinician rates the total improvement on a 7 point scale as follows: 1=very much improved since the initiation of treatment; 2=much improved; 3=minimally improved; 4=no change from baseline (the initiation of treatment); 5=minimally worse; 6= much worse; 7=very much worse since the initiation of treatment.
 
Conners' Continuous Performance Test-3 (CPT-3) - Detectability (d') at Baseline and 2 Months Follow up Conners' Continuous Performance Test-3 (CPT-3) is an objective test of attention and impulsivity that has been validated in individuals aged 8 years and older. d-prime (d') is a measure of how well the respondent discriminates nontargets (i.e., the letter X) from targets (i.e., all other letters). This variable is also a signal detection statistic that measures the difference between the signal (targets) and noise (non-targets) distributions. In general, the greater the difference between the signal and noise distributions, the better the ability to distinguish non-targets and targets. CPT scores are age and gender standardized T-scores, in which the mean is equal to 50 and the standard deviation is equal to 10. d' is reverse-scored so that higher raw score and T-score values indicate worse performance (i.e., poorer discrimination). Atypical scores are higher than 60 indicating "elevated" to "very elevated" performance.
 
Behavior Rating Inventory of Executive Function Adult Version (BRIEF-A) - Metacognitive Index - at Baseline and 2 Months Follow up The Behavior Rating Inventory of Executive Function Adult Version (BRIEF-A) is a standardized measure that captures views of adults' executive functions or self-regulation in their everyday environment. The BRIEF-A comprises 75 items, each rated by the individual, using a 3-point Likert scale ranging from 1 ('Never') to 3 ('Often'). BRIEF-A includes a Behavioral Regulation index, a Metacognition index, and a summary score-Global Executive Composite. The Metacognition Index (MI) reflects the individual's ability to initiate activity and generate problem-solving ideas, to sustain working memory, to plan and organize problem-solving approaches, to monitor success and failure in problem solving, and to organize one's materials and environment. The MI

-------------------------	---

Protocol Synopsis

	subscale includes 40-items with score ranges between 40 to 120. Higher values represent worse outcome and greater difficulties with executive functions.
Other Outcomes	Adverse events will be monitored and documented.
Trial Design and Follow-up Visits Schedule	This study was designed as a pilot single-center, open-label study of 2 months treatment. Following the enrollment, the participants will go through an adjustment process where they will be fitted with a personalized pair of VIZO Glasses. The participants will be instructed to wear the glasses throughout the day for two months. A follow-up visit at the end of the 2-month treatment will be conducted to assess the efficacy of VIZO Glasses on managing ADHD symptoms, using the Conners Continuous Performance Test-3, the Adult ADHD Self-Report Scale (ASRS), Behavior Rating Inventory of Executive Function Adults (BRIEF-A), and Clinical Global Impression-Improvement (CGI-I).
Sample Size	Power analyzes determined that a sample size of 90 participants will have 80% power to detect an effect size of 0.30 (Cohen’s D) using a paired t-test with a 0.05 two-sided significance level. Assuming a 20% attrition rate over the course of the study, 108 participants were targeted for inclusion.
Analysis Plan	
Paired samples t-tests will be used to test the effect of the VIZO-glasses intervention, comparing the baseline and end-of-intervention performances. No corrections for multiple testing will be applied due to the exploratory nature of the study. The safety analysis will include all available data on the intent-to-treat (ITT) population.
 
Paired samples t-tests will be used to test the effect of the VIZO-glasses intervention, comparing the baseline and end-of-intervention performances. Normality distribution of data will be assessed using the Shapiro–Wilk test. Due to the exploratory nature of the study, no corrections for multiple testing will be applied. The safety analysis will include all available data on the intent-to-treat (ITT) population. Additionally, Mixed model ANOVA will was used to explore any potential effect of covariates such as gender, age, eyeglasses, learning disabilities, treatment naïve, and ASRS total score.

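### Does the lack of a stated analysis for the CGI-I secondary endpoint call for a change to the plan?

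*Combined protocol and SAP*

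**What the plan says.** All references are to the combined protocol and SAP.

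- **Endpoints, Secondary.** CGI-I is listed as "Clinical Global Impression-Improvement (CGI-I) - Rate at 2 Months Follow up". The entry explains that "the clinician rates the total improvement on a 7 point scale as follows" and defines all seven points. The midpoint is the null value: "4=no change from baseline (the initiation of treatment". The other endpoints (ASRS total, ASRS inattentiveness, CPT-3 d', BRIEF-A Metacognition Index) are each listed at baseline and at 2 months.
- **Trial Design and Follow-up Visits Schedule.** The closing visit "will be conducted to assess the efficacy of VIZO Glasses on managing ADHD symptoms". CGI-I is the last of the four instruments named for that purpose.
- **Analysis Plan.** The efficacy test is given as: "Paired samples t-tests will be used to test the effect of the VIZO-glasses intervention, comparing the baseline and end-of-intervention performances". A Shapiro–Wilk check and an exploratory mixed model for covariates follow; neither mentions CGI-I. Multiplicity correction is waived because the study is exploratory. The only population named is for safety: "The safety analysis will include all available data on the intent-to-treat (ITT) population".
- **Sample Size.** 90 participants for the paired t-test, then: "Assuming a 20% attrition rate over the course of the study, 108 participants were targeted for inclusion".

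**The concern.** CGI-I is the only efficacy measure rated by a clinician. ASRS and BRIEF-A are self-reported and CPT-3 is a performance test. In an open-label study with one group, a reader may give the clinician's rating particular attention, yet it is the one endpoint that the named test cannot handle: with no baseline value there is nothing to pair.

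Several reasonable analyses remain open: a table of categories, a proportion above some cut-off of improvement, or a one-sample comparison with 4. The word 'rate' in the endpoint title could mean the rating or a response rate. The denominator is open too, since the documents list no CGI-I rating before 2 months and a participant who leaves early would presumably have none. If these options could give materially different answers on the same ratings, the choice could be made after seeing the data, and no multiplicity control would limit it.

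**Working it through.** **1. Does any sentence cover CGI-I?** The paired t-test needs two time points and CGI-I has one. The covariate model and the normality check do not name it. The ITT sentence concerns safety. So the omission is confirmed: no summary, test or denominator is stated.

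**2. The numbers available (Sample Size).** For a paired t-test with effect size 0.30, two-sided alpha 0.05 and n = 90, exact power from the noncentral t distribution is 0.804, so the stated 90 reproduces. The 108 is 90 × 1.2. Losing 20% of 108 leaves 108 × 0.80 = 86.4, about 86 rated and 22 missing. How 108 was derived is a separate matter; both 86 and 90 rated are carried below.

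**3. Effect of the denominator.** Let r be the responder rate among those rated, and assume that dropouts have no CGI-I value. Over all enrolled, with missing counted as not improved, the rate is r × (rated / 108).

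- 86 rated: factor 86/108 = 0.796. The gap is r × (1 − 0.796), or 0.204r.
- 90 rated: factor 90/108 = 0.833. The gap is 0.167r.

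| Rate among rated | Gap, 86 rated | Gap, 90 rated | Exact 95% CI width, 86 rated |
|---|---|---|---|
| 20% | 4.1 points | 3.3 points | 17.8 points (at 17/86) |
| 50% | 10.2 points | 8.3 points | 22.0 points (39.0% to 61.0%, at 43/86) |

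A larger gap arises only when all missing participants counted as failures are set against all counted as responders: 22/108 = 20.4 points, or 18/108 = 16.7 points with 90 rated. That is a bounding exercise, not a choice between two ordinary ways of reporting.

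**4. Effect of the choice of test.** Take n = 86 with k participants rated 3 and all others rated 4. The one-sample t-test is against 4. The exact signed-rank p-value, with zeros dropped and all differences in one direction, is 2 × 0.5^k.

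| k | t-test p | signed-rank p |
|---|---|---|
| 3 | 0.083 | 0.250 |
| 4 | 0.045 | 0.125 |
| 5 | 0.024 | 0.063 |
| 6 | 0.013 | 0.031 |

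The tests fall on opposite sides of 0.05 only at k = 4 and k = 5, when 82 or 81 of 86 participants have not changed. At k = 4 nobody is rated 1 or 2 (0/86, exact 95% CI 0 to 4.2%). That describes the same data and does not contradict a very small mean shift.

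**5. Less extreme ratings.** The documents give no expected distribution, so these sets (n = 90, counts for ratings 1 to 7) are assumptions.

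- Counts 2, 16, 36, 30, 4, 2, 0: mean 3.27. The t-test, signed-rank and sign tests all give p below 0.0001. The proportion rated 2 or better is 18/90 = 20.0%; rated 3 or better, 54/90 = 60.0%.
- Counts 0, 5, 32, 36, 8, 6, 3: mean 3.86. The t-test gives p = 0.22 and the signed-rank test p = 0.19, so they agree. A sign test of 37 improved against 17 worse gives p = 0.009.

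**The case for a change.** The case for a change is that a named efficacy endpoint should have a named analysis, and that two sentences would supply one. Calling the study exploratory explains the absence of multiplicity correction; it does not say how CGI-I will be reported. The options can diverge: the sign test in the second assumed set differs from the other two tests, and in the first set the cut-off moves the proportion from 20.0% to 60.0%. At a 50% rate, the gap between the two ordinary denominators (10.2 points) is close to the half-width of the confidence interval (22.0/2 = 11.0 points).

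What stands is that the plan would be tidier with a CGI-I sentence, and that divergence is possible.

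The rest is weaker. A sign test, a t-test and a proportion past a cut-off answer different questions, so different answers are not a conflict. A table of all seven categories, with the numbers rated and enrolled, lets a reader recover every one of these summaries under either denominator. The missing efficacy population is also not specific to CGI-I. The Analysis Plan names none for ASRS, CPT-3 or BRIEF-A, and a dropout would lack those 2-month values as well, so a CGI-I sentence would leave the broader gap where it is.

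**Conclusion.** The omission is real, but it is missing detail rather than a wrong rule, and it does not call for a change. The endpoint entry fixes the time point, the rater, the seven categories and the value meaning no change. With no applicable test named, the natural course in an exploratory single-group pilot is to tabulate the ratings among those rated. No confirmatory claim depends on a CGI-I p-value.

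The ordinary denominators differ by about 4 to 10 points at response rates of 20% to 50%, within the exact interval widths of about 18 to 22 points. The split between t-test and signed-rank test needs nearly everyone unchanged. These sizes rest on 20% attrition from 108 enrolled and on dropouts having no CGI-I rating. The rating distributions are illustrative, since the documents supply none. The primary analyses, the sample size and the data collected do not depend on the point.

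### The enrolment target of 108 does not keep 90 evaluable participants at 20% attrition; it does so only up to 16.7%

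*Combined protocol and SAP*

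**What the plan says.** The Sample Size row of the Protocol Synopsis makes two linked statements. The first is the power calculation: "Power analyzes determined that a sample size of 90 participants will have 80% power to detect an effect size of 0.30". That effect is expressed as Cohen's d, and the calculation is for a two-sided paired t-test at the 0.05 level. The second statement is the allowance for loss: "Assuming a 20% attrition rate over the course of the study, 108 participants were targeted for inclusion". No inflation formula is shown, and no source is given for the effect size or the attrition rate.

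The Analysis Plan row fixes the efficacy test: "Paired samples t-tests will be used to test the effect of the VIZO-glasses intervention, comparing the baseline and end-of-intervention performances". The Trial Design row provides one follow-up assessment, at the end of the two months. The only sentence on an analysis population concerns safety: "The safety analysis will include all available data on the intent-to-treat (ITT) population". The synopsis gives no imputation rule for missing follow-up scores and no rule for replacing participants who leave.

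**The concern.** An allowance for attrition is meant to leave the required number of evaluable participants once the assumed losses have occurred. Here, 90 evaluable, 20% attrition and 108 enrolled are offered as a consistent set, yet 20% of 108 is more than the 18 participants that separate 108 from 90.

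A paired test cannot use someone without a second measurement, so each loss before the single follow-up visit reduces the efficacy sample. A reader would naturally take the row to mean that 80% power survives 20% attrition. This row is the only justification given for the enrolment number, so its figures should agree with each other.

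**Working it through.** **Inputs, all from the Sample Size row:** d = 0.30; paired t-test; two-sided alpha 0.05; power 80%; n = 90; attrition 20%; target 108. I take d to be the mean change divided by the standard deviation of the changes, which is the version a paired t-test uses. The row does not define it further, but the stated 90 reproduces on this reading.

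**Step 1: reproduce the 90.** Power is the probability that a noncentral t variable, with n − 1 degrees of freedom and noncentrality d√n, falls outside the two-sided 5% critical values. At n = 90 the noncentrality is 0.30 × √90 = 2.846.

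| n | Power for d = 0.30 |
|---|---|
| 86 | 78.5% |
| 87 | 79.0% |
| 88 | 79.5% |
| 89 | 79.9% |
| 90 | 80.4% |

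The smallest n that reaches 80% is 90, so the plan's base figure is exactly right. It also leaves no slack to absorb a shortfall.

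**Step 2: inflate for attrition.** If a fraction a of those enrolled is lost, N enrolled leaves N(1 − a), so N = n / (1 − a).

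- Required: 90 / (1 − 0.20) = 112.5, rounded up to 113. Check: 113 × 0.80 = 90.4.
- Delivered by the stated target: 108 × 0.80 = 86.4.
- Break-even attrition for 108: 1 − 90/108 = 18/108 = 16.7%.
- Likely origin of 108: 90 × 1.20 = 108 exactly. That would be multiplying by 1.2 instead of dividing by 0.8, although the document does not show how it was done.

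**Step 3: size of the effect with 108 enrolled.**

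| Attrition | Completers | Power for d = 0.30 |
|---|---|---|
| 15% | 91 (108 × 0.85 = 91.8, rounded down) | 80.8% |
| 16.7% | 90 | 80.4% |
| 20% | 86 (86.4, rounded down) | 78.5% |
| 25% | 81 | 76.0% |

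The effect detectable with 80% power is 0.306 at n = 86, against 0.2985 at n = 90.

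**Step 4: allow for a random number of completers.** If participants drop out independently, each with probability 0.20 (an assumption; the plan does not say), power averaged over the binomial number of completers is 78.7% for 108 enrolled and 80.5% for 113. The difference is 1.8 points, so the conclusion is unchanged.

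**Step 5: could a different base n explain 108?** The normal approximation gives 87.2, so 88, and 88 / 0.80 = 110, which is still not 108. A base of 86 would give 86 / 0.80 = 107.5, so 108, but 86 has only 78.5% power. The document in any case states 90.

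**The case against.** The strongest reply is about definition. The row does not say what the 20% is a share of. If it means an allowance of 18 on top of the 90 needed (18/90 = 20%), the three figures agree. That reading is possible arithmetically, but an attrition rate over the course of a study ordinarily means a share of those who entered it, and the document offers no other definition. The inconsistency therefore stands under the usual meaning, and that condition should be stated.

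The second reply is about proportion, and much of it stands. The gap is about 1.5 points of power, or 1.0 point if 87 complete. The detectable effect moves from 0.30 to 0.306. Neither d = 0.30 nor the 20% is sourced, and a modest change in either outweighs the gap: at 15% attrition, 108 keeps more than 80% power. The study is an exploratory pilot, and no endpoint, analysis or safety rule depends on the figure. These points limit the importance of the error but do not make the row correct.

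The row is also partly in the past tense, so enrolment may already have been under way or complete. The documents do not settle this. If it was complete, the number actually analysed matters more than the planned inflation.

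Two possible rescues fail. The intent-to-treat sentence covers safety only. The mixed model ANOVA is there to explore covariates and is not the test on which the sample size rests.

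**Conclusion.** The row is wrong as written. With attrition taken as a share of those enrolled, 90 evaluable, 20% attrition and a target of 108 cannot all hold. A target of 108 protects 90 completers only up to 16.7% attrition; at 20% it leaves about 86, with 78.5% power for d = 0.30.

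This rests on the usual definition of attrition, on dropouts having no follow-up score, and on the absence of any imputation or replacement rule. The base power calculation is correct. The error is minor and is not a material loss of power, but it is certain and easily corrected.

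**What to change.** Keep 108 and replace the attrition sentence with one of these:

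- With 20% attrition, about 86 evaluable participants give about 78.5% power for d = 0.30 (80% power for d = 0.306).
- The target of 108 allows for 16.7% attrition (18 losses) while retaining 90 evaluable participants.

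Either wording should say that attrition is counted as a share of those enrolled. The cost is one sentence in the synopsis and a slightly less favourable stated figure: 78.5% instead of 80%, or 16.7% instead of 20%. No extra participants are needed and the analysis does not change. Raising the target to 113 would also make the row consistent, at the cost of five more enrolments (113 − 108), but the small gap in power does not require it.
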